8.2 Statistical Plan Phase II

Phase II considerations:

8.2.1 **Cohort 1**

Cohort 1 (doxorubicin plus pembrolizumab):

Cohort 1: All patients treated in cohort 1 (regardless of dose level) will be included in the efficacy assessments as it is unclear, based on historical data, if there is a significant clinical advantage to higher dose intensity once beyond 50mg/m². Patients with triple negative metastatic breast cancer are eligible. All patients must be doxorubicin and pembrolizumab naïve. Patients will be treated with doxorubicin and pembrolizumab. For each treatment, following the safety lead-in, we will accrue to a total of 36 patients over 18-24months.

Recent (19) data on single agent platinum treatment in first and second line metastatic patients are 25.6% (95% CI 16.8-36.1%), with second line cisplatin at 22.2% and first-line carboplatin at 22.9%. First-line patients who will be likely candidates for this study will either have peripheral neuropathy preventing taxanes and platinum, or will have recurred rapidly after taxane-platinum containing adjuvant therapy, or progressed, suggesting low efficacy of standard approach. Patients would need to be doxorubicin naïve. As a result of this patient selection, we have set a discouraging response rate at 15% and an encouraging rate at 34%. The null hypothesis H0: is ORR≤=15%, and the alternative H1: ORR≥=34%. Specifically, for we follow Simon’s MinMax two-stage design with a type I error of 10% and a power of 90%: If 3 or fewer responses are noted in the first 22 patients in this cohort, the study will hold accrual for futility. In the case of early stopping, evaluation of patient subsets (e.g. immune phenotype), in consultation with the PI, statistician, sponsor and DSMB, may permit the study to continue for specific subsets following an amendment if it is deemed to be inadequately evaluated and there appears to be sufficient promise for that subset. If early stopping does not occur, accrual will continue to a total of 36 patients are treated in this cohort. With 36 patients, 9 patients with an ORR (25%) are required to deem this combination worthy of further evaluation. This maintains the type I error at 10% to reject the null hypothesis and the power at 90% to declare a positive finding if the alternative hypothesis holds. Secondary analysis endpoints, including progression-free survival, time-to-treatment failure, and toxicity may influence the overall recommendation for future evaluation. With 36 patients on this cohort, we expect at least 10 patients on this cohort to have pre- and post-treatment biopsy material for correlative analysis and approximately 36 patients with pre-treatment biopsy.

8.2.2 Cohort 2

Cohort 2 (AI+pembrolizumab): Patients with ER+ HR2- metastatic breast cancer who have recurred on or after, or progressed on prior endocrine therapy. Objective response in this setting is rare for AI (~10%), which has suggested the following design:

We will accrue 20 patients over 12-24 months. With 20 patients, if 3 or more patients experience a response, this would be considered worthy of further evaluation. This rule has a power of over 80% to detect a true response rate of 20% (encouraging, alternative hypothesis) and a type I error of less than 8% for falsely declaring a 5% response rate (discouraging, null hypothesis) as promising. This rule establishes the minimum response rate for declaring the combination promising, however, it does not preclude the combination could be promising based on secondary endpoints such as progression-free survival. Analysis by prior treatment may also influence the overall recommendation.

In addition, with 20 patients in this cohort, we expect to obtain at least 10 patients with pre and post-treatment biopsy for correlative analysis, although all patients will have tissue for baseline evaluation.

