5.0 METHODOLOGY

5.1 Entry Criteria

5.1.1 Diagnosis/Condition for Entry into the Trial

Patients who are 18 years or older with 1) stage IV metastatic triple negative breast cancer (triple negative is defined as ER and PgR status is <1% of tumor cell nuclei are immunoreactive for ER or PgR, and HER2 status is FISH negative or IHC 0 or 1+) or 2) Stage IV HR+ HER2- (HR+) breast cancer (defined as ER or PgR $\geq 1\%$ of tumor cell nuclei are immunoreactive for ER or PgR and HER2 status is FISH negative or ICH 0 or 1+).

Subject Inclusion Criteria

In order to be eligible for participation in this trial, the subject must:

1. Be willing and able to provide written informed consent/assent for the trial.
2. Be ≥ 18 years of age on day of signing informed consent.
3. Have measurable disease based on RECIST 1.1.
4. Be willing to provide tissue from a newly obtained core or excisional biopsy of a tumor lesion. *Newly-obtained is defined as a specimen obtained up to 6 weeks (42 days) prior to initiation of treatment on Day 1. Subjects for whom newly-obtained samples cannot be provided (e.g. inaccessible or subject safety concern) may submit an archived specimen only upon agreement from the Sponsor.*
5. Have a performance status of 0 or 1 on the ECOG Performance Scale.
6. Demonstrate adequate organ function as defined in Table 1, all screening labs should be performed within 7 days of treatment initiation.

Table 1 Adequate Organ Function Laboratory Values

System	Laboratory Value
Hematological	
Absolute neutrophil count (ANC)	$\geq 1,500$ /mcL
Platelets	$\geq 100,000$ / mcL
Hemoglobin	≥ 9 g/dL or ≥ 5.6 mmol/L without transfusion or EPO dependency (within 7 days of assessment)
Renal	
Serum creatinine OR	≤ 1.5 X upper limit of normal (ULN) OR

Measured or calculated ^a creatinine clearance (GFR can also be used in place of creatinine or CrCl)	≥ 60 mL/min for subject with creatinine levels $> 1.5 \times$ institutional ULN
Cardiac	
Left ventricular ejection fraction by MUGA or Echocardiogram [#]	$\geq 55\%$; \geq upper limit of institutional normal
Hepatic	
Serum total bilirubin	$\leq 1.5 \times$ ULN OR Direct bilirubin \leq ULN for subjects with total bilirubin levels > 1.5 ULN
AST (SGOT) and ALT (SGPT)	$\leq 2.5 \times$ ULN OR $\leq 5 \times$ ULN for subjects with liver metastases
Albumin	> 2.5 mg/dL
Coagulation	

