5.1.2 Subject Exclusion Criteria

The subject must be excluded from participating in the trial if the subject:

1. Cohort 1: Has triple negative breast cancer, is considered for cohort 1 participation, and received prior anthracycline therapy.
Cohort 2: Has received prior aromatase inhibitor therapy and is deemed to be resistant to all three (anastrozole, letrozole, exemestane) approved AIs. Resistance is defined as progression within 12 months or while on an AI.
2. Patient is premenopausal (see Table 1, medical ovarian suppression is allowed)Is currently participating and receiving study therapy or has participated in a study of an investigational agent and received study therapy or used an investigational device within 4 weeks of the first dose of treatment.
3. Has a diagnosis of immunodeficiency or is receiving systemic steroid therapy or any other form of immunosuppressive therapy within 7 days prior to the first dose of trial treatment.
4. Has a known history of active TB (Bacillus Tuberculosis)
5. Hypersensitivity to pembrolizumab or any of its excipients.
6. Suboptimal cardiac function as defined by decreased left ventricular ejection fraction < 55% for cohort 1, and < 50% for cohort 2.
7. Prior pembrolizumab.
8. Has had a prior anti-cancer monoclonal antibody (mAb) within 4 weeks prior to study Day 1 or who has not recovered (i.e., \leq Grade 1 or at baseline) from adverse events due to agents administered more than 4 weeks earlier.
9. Has had prior chemotherapy, targeted small molecule therapy, or radiation therapy within 2 weeks prior to study Day 1 or who has not recovered (i.e., \leq Grade 1 or at baseline) from adverse events due to a previously administered agent.
 - Note: Subjects with \leq Grade 2 neuropathy are an exception to this criterion and may qualify for the study.

- Note: If subject received major surgery, they must have recovered adequately from the toxicity and/or complications from the intervention prior to starting therapy.

10. Has a known additional malignancy that has progressed or required active treatment in the past 5 years. Exceptions include basal cell carcinoma of the skin or squamous cell carcinoma of the skin that has undergone potentially curative therapy or in situ cervical cancer.

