5.2.4 Registration procedure

To register a participant, the subsequent procedure is to be followed.

1. The coordinator/research nurse should contact the DCC via telephone or email to provide notification regarding the pending registration and communicate desired timeline of the registration, especially if it must be completed promptly.

2. The coordinator/research nurse should then e-mail copies to [contact] of the following documents to the DCC:

- Completed Eligibility Criteria List (printed from Section 5.1.1 and 5.1.2 of the protocol)
- Source documentation to support eligibility criteria**
- Signed informed consent document
- Signed HIPAA authorization form (if separate from the informed consent document)
- Signed subject's Bill of Rights (COH only)

**For COH participants, provide copies of source documentation only if not readily available as a finalized record in the COH EMR.

3. After having received all documentation, the DCC will complete the review the documents to verify eligibility, working with the staff as needed to resolve any missing required source elements. A subject failing to meet all protocol eligibility requirements will not be registered.

4. Once eligibility has been confirmed, DCC staff will register the participant by assigning a participant study number and will enter the subject into the eCRF system, Medidata RAVE (once dosing is confirmed). The COH CRC will directly accession into MIDAS as per current policy and procedure.

5. Once registration has been completed, DCC staff will send a Confirmation of Registration Form, including the participant study number and cohort assignment to:

- the site study team: site PI, treating physician, biostatistician, protocol nurse, CRC and IDS pharmacy.

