5.3 Trial Treatments

The treatment to be used in this trial is outlined below in [Table 2](#)

Table 2 Trial Treatment

Cohort 1 Triple negative breast cancer

Drug	Dose	Dose Frequency	Route of Administration	Regimen/Treatment Period	Use
Pembrolizumab	200 mg	Q3W	IV infusion	Day 1 of each 3 week cycle	Experimental
Doxorubicin*	50-60 mg/m ²	Q3W X 6 cycles	IV infusion	Day 1 of each 3 week cycle, standard	

*starting dose 50 mg/m² for cohort 1, escalating to 60mg/m² based on acceptable toxicity during safety-lead in. see Statistical Section. No intrapatient dose escalation

is allowed. After 6 cycles of doxorubicin and pembrolizumab, patients will continue on pembrolizumab alone up to a total of 24 cycles.

Subjects who stop pembrolizumab with stable disease or better may be eligible for up to one year of additional pembrolizumab therapy if they progress after stopping study treatment.

Cohort 2 HR+ breast cancer

Drug	Dose/Potency	Dose Frequency	Route of Administration	Regimen/Treatment Period	Use
Pembrolizumab	200 mg	Q3W	IV infusion	Day 1 of each 3 week cycle	Experimental
Aromatase inhibitor (AI)*	Exemestane 25 mg daily po preferred, Anastrozole 1 mg daily po, or letrozole 2.5 mg daily po are options	QD	Po	QD cycle, standard	

*pending prior exposure: patients could not have failed all three commercially available AIs.

Trial treatment should begin as close as possible to the date on which treatment is allocated/assigned.

Subjects who stop pembrolizumab with stable disease or better may be eligible for up to one year of additional pembrolizumab therapy if they progress after stopping study treatment.

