7.1.1.5.2 Prior Treatment Details

The investigator or qualified designee will review all prior cancer treatments including systemic treatments, radiation and surgeries.

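### The Cohort 2 response benchmark in 8.2.2 assumes recurrence or progression after endocrine therapy, but the 5.1 criteria checked at registration do not require it, so endocrine-naive patients can count toward the 3-of-20 rule

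*Combined protocol and SAP*

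**What the plan says.** Section 8.2.2 gives the Cohort 2 population as "Patients with ER+ HR2- metastatic breast cancer who have recurred on or after, or progressed on prior endocrine therapy". It puts objective response to an AI in that setting at about 10% and takes the design from there: 20 patients, 3 or more responses to call the combination promising, a discouraging rate of 5% with type I error below 8%, and an encouraging rate of 20% with power above 80%.

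The entry criteria are in section 5.1. For Cohort 2, section 5.1.1 asks for "2) Stage IV HR+ HER2- (HR+) breast cancer (defined as ER or PgR" at least 1%, plus general criteria. Table 1 adds postmenopausal status; where it mentions tamoxifen or an AI, this serves only to decide who needs hormone testing. The one Cohort 2 rule on endocrine history is exclusion 1 in section 5.1.2: "Has received prior aromatase inhibitor therapy and is deemed to be resistant to all three (anastrozole, letrozole, exemestane) approved AIs". The Table 2 footnote in section 5.3 repeats it: "pending prior exposure: patients could not have failed all three commercially available AIs".

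Under section 5.2.4 the registering staff submit a "Completed Eligibility Criteria List (printed from Section 5.1.1 and 5.1.2 of the protocol", and step 3 says "A subject failing to meet all protocol eligibility requirements will not be registered".

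The hypothesis in section 3.1 speaks of a mainly endocrine-resistant group. The rationale in section 4.1.3 expects most eligible patients to have had a non-steroidal AI already. Section 8.2.2 adds that an analysis by prior treatment may bear on the recommendation, without naming subgroups, a method or a rule.

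**The concern.** Exclusion 1 is a ceiling on prior endocrine treatment, with no floor. A patient who has never had endocrine therapy passes every listed item, and step 3 of registration has nothing in 5.1 against which to refuse her. Section 8.2.2 defines no analysis set that would take her out of the 20.

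Cohort 2 has no control arm and a bar of three responses. A response that such a patient would have had to the AI alone is one of the three. The rule's error and power are stated for a pretreated population, so they need not hold for the population that 5.1 admits.

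**Working it through.** **1. The plan's own figures.** Inputs from 8.2.2: n = 20, bar of 3, rates 5% and 20%. With X ~ Binomial(20, p), P(X ≥ 3) = 1 − P(0) − P(1) − P(2).

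- p = 0.05: 1 − 0.3585 − 0.3774 − 0.1887 = 0.0755 before rounding of the terms. This agrees with the stated type I error below 8%.
- p = 0.20: 1 − 0.0115 − 0.0576 − 0.1369 = 0.7939. The stated power is above 80%; the exact value is 79.4%.
- p = 0.10, the plan's AI-alone rate: 1 − 0.1216 − 0.2702 − 0.2852 = 0.3231 before rounding of the terms.

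**2. A mixed cohort.** Let m of the 20 be endocrine-naive with response rate x, and let the other 20 − m respond at a base rate b. The total is Binomial(m, x) + Binomial(20 − m, b), and P(total ≥ 3) follows by exact convolution. The documents give neither m nor x. Assumed ranges: m = 1 to 3 and x = 15% to 40%, with x = 10% as a floor.

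For m = 1 the formula is P(Y ≥ 3) + x·P(Y = 2), with Y ~ Binomial(19, b). At b = 0.10 this is 0.2946 + 0.2852x, which gives 0.337 at x = 0.15 and 0.409 at x = 0.40.

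| Naive patients (m) | b = 10%, x = 10% | b = 10%, x = 15-40% | b = 5%, x = 10% | b = 5%, x = 15-40% |
|---|---|---|---|---|
| 0 | 32.3% | 32.3% | 7.5% | 7.5% |
| 1 | 32.3% | 34-41% | 8.4% | 9-14% |
| 2 | 32.3% | 35-50% | 9.4% | 11-23% |
| 3 | 32.3% | 37-58% | 10.4% | 14-33% |

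The two base rates answer different questions. The 10% base is the one consistent with the plan's statement about an AI alone. The 5% base shows only how far the rule departs from its nominal design null; it does not describe AI treatment without a pembrolizumab effect.

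**3. The rule applied only to patients who meet the 8.2.2 definition**, bar of 3 unchanged:

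| Qualifying patients | Error at 5% | Power at 20% |
|---|---|---|
| 20 | 7.5% | 79.4% |
| 19 | 6.7% | 76% |
| 18 | 5.8% | 73% |
| 17 | 5.0% | 69% |

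**The case against.** The best reply is that the population is not undefined. Section 8.2.2 states it in the same combined document, sections 3.1 and 4.1.3 point the same way, and nothing in 5.1 says the opposite. Registration refers to all protocol eligibility requirements, and under section 7.1.1.5.2 the investigator or designee "will review all prior cancer treatments including systemic treatments, radiation and surgeries". This shows the intent and stands to that extent. A reader might infer that 5.1 contradicts 8.2.2 or deliberately admits naive patients; the documents do not support that, because 5.1 is only silent. But the checklist is printed from 5.1.1 and 5.1.2. If 8.2.2 is the restriction, the checklist omits it; if it is not, the benchmark does not match the eligible population. Either reading needs reconciling.

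A second reply concerns size. The naive share and the naive response rate are assumptions, and section 4.1.3 suggests that few naive patients will enter. This stands in full. On the 10% base most of the false-positive risk (32.3%) is there with no naive patients at all, because the 5% null lies below the plan's own AI rate.

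A third concerns Cohort 1. Section 8.2.1 says "All patients must be doxorubicin and pembrolizumab naïve", and 5.1.2 carries this as exclusions 1 and 7. A reader might infer that only the Cohort 2 condition was overlooked. The documents do not support that: the first-line patient selection behind the 15% and 34% rates for Cohort 1 (neuropathy, rapid recurrence or progression) is not in 5.1 either.

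**Conclusion.** The gap in the text is real and should be fixed; confidence in that part is high. Under the plan as written, responses from endocrine-naive patients can count toward a rule set for patients who recurred or progressed after endocrine therapy.

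The size of the effect is not known from the documents. Under the assumptions above it ranges from nothing (naive patients also at about 10%, others at 10%) to a rise from 32.3% to 58% (three naive patients at 40%, others at 10%). A reader might take the larger figures as the trial's actual false-positive rate, or the 5%-base figures as what an AI alone would produce. Neither holds: the first rests on assumed inputs, and the second conflicts with the 10% stated in 8.2.2.

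The 5% null set below the stated AI rate is a separate issue, which the fix here does not cure.

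**What to change.** Reconcile 5.1 with 8.2.2.

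- **Simplest route.** Add to 5.1.1, as a Cohort 2 inclusion criterion, only the clause of 8.2.2 that requires recurrence on or after, or progression on, earlier endocrine treatment. Do not move the whole sentence: it names ER+ disease, while 5.1.1 accepts ER or PgR. The receptor definition, n = 20 and the bar of 3 stay. Cost: one eligibility line by amendment and possibly slower accrual. The clause has no time limit, so it secures prior endocrine exposure, not resistance or prior AI use.
- **If the sponsor means to admit endocrine-naive patients.** Restate the population, benchmark rates and operating characteristics in 8.2.2. This leaves eligibility alone but needs a response rate for naive patients, which the documents do not give.
- **If naive patients are already enrolled.** Classify every Cohort 2 patient from the baseline prior-treatment records without reference to response, since the trial is open-label (5.3.5). Report response in both groups, and state the exact error and power of the 3-response rule for the number who qualify, from the second table. This adds no patients; power at 20% falls from 79.4% to 76%, 73% or 69% with one, two or three naive patients.

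In any of these, correct the stated power of over 80% to 79.4% for n = 20.

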3.2.2 To assess feasibility and toxicity

Hypothesis: A combination of pembrolizumab and doxorubicin in patients with TN breast cancer will provide favorable outcomes vs. the expected single agent response rate with either agent alone, and the combination will have a favorable toxicity profile/risk-benefit ratio.

(3) Objectives:

3.2.3 To assess clinical benefit rate (lack of progression for > 24 weeks), duration of response, time-to-treatment failure, progression-free survival, and overall survival in patients with stage IV HR+ breast cancer based primarily on RECIST 1.1, and irRECIST.

(4) 3.2.4 To assess feasibility and toxicities.

Hypothesis: A combination of pembrolizumab and an aromatase inhibitor in patients with HR+ breast cancer will provide favorable outcomes vs. the expected single agent response rate with an aromatase inhibitor, or with pembrolizumab alone, and the combination will have a favorable toxicity profile/risk-benefit ratio.

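### Cohort 2's 3-of-20 rule passes about 32% of the time at the ~10% AI response rate the plan cites, which Section 8.2.2 does not report, and its stated power of over 80% is 79.4%

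*Combined protocol and SAP*

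**What the plan says.** Section 8.2.2 gives the starting point for Cohort 2 (AI plus pembrolizumab): "Objective response in this setting is rare for AI (~10%), which has suggested the following design". The design is a single arm in one stage: "We will accrue 20 patients over 12-24 months", and "if 3 or more patients experience a response, this would be considered worthy of further evaluation".

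Two operating characteristics follow. For power, the text reads "This rule has a power of over 80% to detect a true response rate of 20" percent, the rate labelled encouraging. For false positives, it claims "a type I error of less than 8% for falsely declaring a 5% response rate (discouraging, null hypothesis) as promising". The section adds: "This rule establishes the minimum response rate for declaring the combination promising". It leaves room for secondary endpoints, and for analysis by prior treatment, to influence the recommendation.

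Section 3.2 gives the Cohort 2 hypothesis, which is that the combination "will provide favorable outcomes vs. the expected single agent response rate with an aromatase inhibitor, or with pembrolizumab alone".

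**The concern.** The rate that prompted the design (about 10%) and the rate at which the false-positive probability is reported (5%) differ by a factor of two, and Section 8.2.2 does not explain the step. Cohort 1 also sets its null (15%) below its cited benchmark (25.6%), but Section 8.2.1 gives patient selection as the reason. In Cohort 2 the 10% is already described as the rate in this setting, and no further adjustment is offered.

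A 5% null is a legitimate choice for a screening rule. What is missing is how the rule behaves at the plan's own benchmark. The trial has no control arm, so the historical AI rate is the only AI comparator available, and the 3-of-20 rule is the only response criterion for this cohort. A reader given only the figure of under 8% could take a positive Cohort 2 as evidence that pembrolizumab adds to the AI.

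The power statement is a separate and smaller matter. It makes a directional claim about the cohort's primary endpoint, and the exact value falls on the other side of 80%.

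**Working it through.** **Inputs (Section 8.2.2):** n = 20; success at 3 or more responses; null 5%; alternative 20%; cited AI rate about 10%.

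**Formula.** With X binomial(20, p),

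P(X ≥ 3) = 1 − (1−p)^20 − 20·p·(1−p)^19 − 190·p²·(1−p)^18.

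**1. The plan's own figures**

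- p = 0.05: 1 − 0.35849 − 0.37735 − 0.18868 = 0.0755. The stated bound of 8% holds.
- p = 0.20: 1 − 0.01153 − 0.05765 − 0.13691 = 0.7939. The stated power of over 80% does not hold; the shortfall is 0.6 points. P(X ≥ 3) first reaches 0.80 at p = 0.202.

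A neighbouring sample size does not make both statements true:

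| n | P(≥3) at 5% | P(≥3) at 20% |
|---|---|---|
| 19 | 6.7% | 76.3% |
| 20 | 7.5% | 79.4% |
| 21 | 8.5% | 82.1% |

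At n = 21 the power passes 80%, but type I error is no longer below 8%.

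**2. The pass rate at the cited AI rate**

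- p = 0.10: 1 − 0.12158 − 0.27017 − 0.28518 = 0.3231.

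This is 0.3231 / 0.0755 = 4.3 times the rate at 5%. Because the plan gives 10% only as approximate, the range around it (8% and 12% are my assumptions) is:

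| True response rate | P(≥3 of 20) |
|---|---|
| 5% (plan's null) | 7.55% |
| 8% | 21.2% |
| 10% (cited for AI) | 32.3% |
| 12% | 43.7% |
| 20% (plan's alternative) | 79.4% |

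**3. What the smallest passing result shows**

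3/20 = 15%, with an exact (Clopper–Pearson) 95% confidence interval of 3.2% to 37.9%. The interval contains 10%.

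**4. Why the threshold is not the thing to change**

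With n = 20, requiring 4 responses lowers the pass rate at 10% to 13.3% but cuts power at 20% to 58.9%. Requiring 5 gives 4.3% and 37.0%. Twenty patients cannot separate 10% from 20% with conventional error rates, so the remedy is to report the limit rather than move the cut-off.

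**The case against.** The strongest reply is that only one statement is false, and it is off by 0.6 points. The type I error is right at the null the plan names, both error rates are given at the named null and alternative, and a pass rate at a third value is an optional extra. Section 8.2.2 claims only that a pass merits further evaluation, calls the rule a minimum, and lets secondary endpoints and prior treatment bear on the recommendation. The Section 3.2 hypothesis sits under the secondary objectives, speaks of outcomes and toxicity generally, and is not tied to the 3-of-20 rule.

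The 10% is also soft. It is approximate and uncited in Section 8.2.2. The other HR+ response rate of about 10%, in the rationale section, is for letrozole plus palbociclib. Section 5.1.2 excludes only patients resistant to all three AIs, so the AI-alone rate among those enrolled is not settled.

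Finally, an interval that covers the benchmark at the cut-off is ordinary in small designs. The intervals for 4/20 (5.7% to 43.7%) and 5/20 (8.7% to 49.1%) also contain 10%; 6/20 (11.9% to 54.3%) is the first that does not. Cohort 1's minimum pass, 9/36 (12.1% to 42.2%), contains its own 15% null.

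Much of this stands. The design is not invalid, the 5% null is permissible, 32% is not the type I error, and the interval adds context rather than separate proof of a fault. The reply does not rescue the power statement. Nor does it justify leaving out the pass rate at the one AI benchmark the section says prompted the design, when the hypothesis is worded against the AI response rate. The softness of 10% is a reason to give a range; even at 8% the pass rate is 21.2%, nearly three times the reported figure.

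**Conclusion.** The concern holds and should be fixed. Power at a true response rate of 20% is 79.4%, not above 80%. This is a small error that affects neither the sample size nor the threshold. The more consequential part is the omission: at the cited AI rate the rule is met 32.3% of the time (21.2% at 8%, 43.7% at 12%), against the 7.55% behind the only figure reported. Meeting the rule can justify further evaluation, but it cannot by itself support a claim of improvement over an AI alone.

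These figures assume 20 evaluable patients, independent responses with a common probability, and the plan's approximate 10% as the AI rate. The power correction does not depend on that last assumption; the 32% does.

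**What to change.** Keep n = 20 and the threshold of 3 responses. In Section 8.2.2:

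1. Replace the power statement with: *a power of about 79% (79.4%) at a true response rate of 20%*.
2. After the type I error at 5%, add: *If the true response rate equals the approximately 10% cited above for AI, the probability of meeting this rule is about 32% (21% at 8%, 44% at 12%). Meeting the rule supports further evaluation only and does not show improvement over AI alone; 3 responses in 20 has an exact 95% confidence interval of 3.2% to 37.9%.*

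The cost is two wording changes, with no extra patients and no change to the go/no-go decision. The stated figures will look slightly less favourable, and the conclusion from a positive Cohort 2 will be narrower.
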